The nonclinical safety profile of ZN-c5 has been well characterized through the conduct of single- and repeat-dose studies of up to 13 weeks in duration. The primary target organ effects in repeat dose studies were related to reproductive tissues and the liver. Microscopic findings in the bone marrow in high-dose treated dogs in the 28-day study consisted of decreased erythropoiesis which correlated with the hematology finding of decreased reticulocyte counts, secondary to inflammation. These effects were not seen in the 13-week repeat dose dog study. The liver effect in the 28-day dog study was associated with cholestasis leading to hyperbilirubinemia, most likely due to inhibition of the bile salt export pump (BSEP) in vitro, with an IC₅₀ of 20.2 μM. These liver effects were not observed in the 13week dog study. In the 14-day rat study, the liver effects were limited to microvesicular changes due to lipid deposition in hepatocytes as confirmed with oil--red--O staining. This effect in rats is most likely due to the anti-estrogenic effect of ZN-c5 given that estrogen plays an important role in lipid homeostasis within the liver. Effects of ZN-c5 on sex organs (decreased uterine weights, development of ovarian cysts, hypertrophy and hyperplasia of the mammary gland, prostate atrophy, testicular degeneration) are postulated to also be due to the pharmacological effect of the test article. This includes the effects seen in the male dog testes. The non-glandular stomach changes noted in the rat are not a risk to humans as humans lack a non-glandular stomach. The potential for reversibility of all adverse effects was established following a 1-month non-dosing period. All the adverse effects reversed or showed evidence of reversibility, except for the testicular effects in dogs that did not exhibit any signs of recovery.

In the safety pharmacology endpoints captured during the repeat dose toxicology studies, ZN-c5 did not exhibit any adverse CNS effects based on the functional observation battery (FOB), and no respiratory findings in the repeat dose toxicology studies or in a stand-alone respiratory study. In addition, there were no cardiovascular effects based on monitoring of electrocardiogram (ECG) parameters in the 28-day dog study or in a definitive cardiovascular study in dogs with telemetry implants. In addition, ZN-c5 was negative in the in vitro and in vivo genetic toxicology studies.

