9.4.4.3 LABORATORY EVALUATIONS

All laboratory data will be listed. Summaries of laboratory data will be based on observed data. The focus of laboratory data summarization will be on treatment-emergent laboratory abnormalities. A treatment-emergent laboratory abnormality is defined as an abnormality that, compared to baseline, worsens by ≥ 1 grade in the period from the first dose of study drug to 30 days after the last dose of study drug. If baseline data are missing, then any graded abnormality (i.e., an abnormality that is Grade ≥ 1 in severity) will be considered treatment-emergent.

Hematological, serum biochemistry, and urine data will be programmatically graded according to CTCAE severity grade, when applicable. For parameters for which a CTCAE scale does not exist, reference ranges from the local laboratory will be used to determine programmatically if a laboratory parameter is below, within, or above the normal range for the subject's age, sex, etc. Hematological and serum biochemistry and their changes from baseline will be summarized by dose level, by visit. Summary tables will be presented for each relevant assay to show the number of subjects by CTCAE severity grade with corresponding percentages. For parameters for which a CTCAE scale does not exist, the frequency of subjects with values below, within, and above the normal ranges will be summarized. Subjects will be characterized only once for a given assay, based on their worst severity grade observed during a period of interest (e.g., during the study or from baseline to a particular visit).

Shift tables for hematology and serum biochemistry will also be presented by showing change in CTCAE severity grade from baseline to the worst grade post-baseline. For parameters for which a CTCAE scale does not exist, shift tables will be presented showing change in results from baseline to the worst grade post baseline. Separate listings and summaries will be prepared for laboratory abnormalities that are C Grade C 3 in severity.

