3.7 Schedule of Assessments

Table 2 Time and Events Schedule

Study Phase	Screening	Cycle 1 (28-day cycle)					Cycles \geq 2 (28-day cycle)		EOT	30-day Safety Follow-up	Disease Assessment Follow-up ²¹ (every 12 weeks)	Survival Follow-up ²² (every 12 weeks)
Cycle Day	Day -28	Day 1	Day 2	Day 8	Day 15	Day 16	Day 1	[Day 15* Cycle 2 Combination only]				
Window (days)	-28 to -1			± 1	± 2		$[\pm 4^{23}]$	$[\pm 2]$	± 7	± 7	± 7	± 14
Informed Consent	X											
Medical and Medication History ¹	X											
Physical Examination ²	X	X		X	X		X	[X]	X	X		
ECOG Performance Status	X	X					X	[X]	X	X		
Vital Signs ³	X	X		X	X		X	[X]	X	X		
TriPLICATE 12-lead ECG ⁴	X	X	[X]		X	[X]	[X]		X			
Adverse events/ Concomitant medications ⁵	[X]	X	[X]	X	X	[X]	X	[X]	X	X		
Enrollment	X											
Hematology	X ⁷	X		X	X		X	[X]	X	X		
Chemistry	X ⁷	X		X	X		X	[X]	X	X		
Coagulation ⁸	X ⁷								X			
Full Lipid Panel ⁹		[X]					[X]					

Study Phase	Screening	Cycle 1 (28-day cycle)					Cycles ≥ 2 (28-day cycle)		EOT	30-day Safety Follow-up	Disease Assessment Follow-up ²¹ (every 12 weeks)	Survival Follow-up ²² (every 12 weeks)
Cycle Day	Day -28	Day 1	Day 2	Day 8	Day 15	Day 16	Day 1	[Day 15* Cycle 2 Combination only]				
Window (days)	-28 to -1			± 1	± 2		[± 4 ²³]	[± 2]	± 7	± 7	± 7	± 14
Urinalysis ¹⁰	X ⁷								X			
Pregnancy Test ¹¹	X	X					X		X	X		
PK ¹²		[X]	[X]	[X]	[X]	[X]	[X]					
ZN-c5 pharmacodynamic and exploratory biomarkers in blood ¹³		X					X		[X]		[X]	
Tumor Biopsy ¹⁴	[X]						[X]		[X]		[X]	
ESR1 Mutation ¹⁵		X					X		[X]		[X]	
CT/MRI ¹⁶	X						X		X		[X]	
4β-hydroxycholesterol / cholesterol ¹⁷		X			X		X					
FES-PET ¹⁸	[X]						[X]					
ZN-c5 oral dosing ¹⁹		X										
Palbociclib oral dosing (Combo only) ²⁰		[X]										

Study Phase	Screening	Cycle 1 (28-day cycle)					Cycles ≥ 2 (28-day cycle)		EOT	30-day Safety Follow-up	Disease Assessment Follow-up ²¹ (every 12 weeks)	Survival Follow-up ²² (every 12 weeks)
		Day -28	Day 1	Day 2	Day 8	Day 15	Day 16	Day 1				
Cycle Day	Day -28	Day 1	Day 2	Day 8	Day 15	Day 16	Day 1	[Day 15* Cycle 2 Combination only]				
Window (days)	-28 to -1			± 1	± 2		[± 4 ²³]	[± 2]	± 7	± 7	± 7	± 14
Subject Dosing Diary Accountability and/or Dispensing ⁶		X					X		X			
LTFU ²²												[X]

Notes: X = Required; [X] = Only applicable as per footnote as indicated by the Assessment

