6.6.4 Laboratory Data

Laboratory assessments include:

Table 4 Laboratory Tests

Category	Parameters
Hematology	Hemoglobin, hematocrit, platelet count, WBC count with differential (neutrophils, eosinophils, basophils, lymphocytes, monocytes)
Coagulation	PT/INR, aPTT
Serum Chemistry	Total protein, albumin, BUN, creatinine, calculated CrCl, total bilirubin with direct bilirubin as applicable, AST (SGOT), ALT (SGPT), alkaline phosphatase, GGT, glucose, sodium, potassium, chloride, calcium, magnesium, phosphate, full lipid panel
Urinalysis	visual inspection, microscopic examination, and dipstick test for pH, protein, glucose, WBC, bilirubin, and blood
Pregnancy Test	β-hCG (for women of childbearing potential) During Screening, a serum pregnancy test must be performed. During the study, urine or serum pregnancy tests can be performed.

ALT = alanine aminotransferase; aPTT = activated partial thromboplastin time; AST = aspartate aminotransferase; β -hCG = beta-human chorionic gonadotropin; BUN = blood urea nitrogen; CPK = creatine phosphokinase; CrCl = creatinine clearance; GGT = gamma-glutamyl-transferase; PT/INR = Prothrombin Time – International Normalized Ratio; SGOT = serum glutamic-oxaloacetic transaminase; SGPT = serum glutamic pyruvic transaminase; WBC = white blood cell

A full lipid panel, regardless of fasting status, will be performed on C1D1, C3D1 (coinciding with the first on-study tumor assessment after 8 weeks) and C7D1 (6 months into the study). This will not be assessed in the Monotherapy Phase 2 part of the study.

In addition: Plasma 4 β -hydroxycholesterol and cholesterol will be analyzed (from the same blood draw as for PK) at the following time points of the Monotherapy Dose Escalation and Expansion cohorts:

[Cycle 1 Day 1] pre-dose (0 hr)

[Cycle 1 Day 15] pre-dose (0 hr)

[Cycles 2, 3 and 4 Day 1] pre-dose (0 hour)

All laboratory data will be stored in the database with the units in which they are originally reported. Laboratory data in summary tables and subject data listings will be presented in the International System of Units (SI units; Système International d’Unités).

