Hematology, serum chemistry and coagulation tests will be programmatically graded according to NCI-CTCAE v4.03 toxicity grading as detailed in [Appendix 1 NCI-CTCAE V4.03 Toxicity Grading](#) when applicable. For parameters for which a CTCAE scale does not exist, reference ranges from the local laboratory will be used to determine programmatically if a laboratory parameter is below, within or above the normal range for the subject’s age, sex, etc.

Treatment-emergent laboratory abnormalities will be identified and will be the focus of laboratory data summarization. A treatment-emergent laboratory abnormality is defined as an abnormality that, compared to baseline, worsens by ≥ 1 grade in the period from the first dose of study drug to 30 days after the last dose of study drug. If baseline data are missing, then any graded abnormality (i.e., an abnormality that is Grade ≥ 1 in severity) will be considered treatment-emergent.

For laboratory results entered with inequality symbols ($<$, \leq , $>$, \geq), numeric values will be imputed by ignoring the inequality symbol(s) (e.g. “ <1.71 ” will be imputed as 1.71 for numeric analyses). Imputed values will not be listed in data listings.

For each laboratory test, Baseline and worst (maximum) CTCAE grade post-Baseline will be identified for each subject. For parameters for which a CTCAE scale does not exist, the Baseline and worst post-Baseline value will be identified as being below, within or above the normal range as detailed above. Change from Baseline will be calculated for all post-Baseline results.

Subjects will be characterized only once for a given assay, based on the worst severity grade observed during a period of interest (e.g., during the study or from Baseline to a particular visit).

Hematology, coagulation and serum chemistry data, and changes from Baseline will be summarized by dose level, by visit for visits from Baseline to C2D1 as well as EOT. Urinalysis and pregnancy test results will be listed only. Plasma 4 β -hydroxycholesterol and cholesterol will be listed only.

Shift tables for hematology, coagulation and serum chemistry will also be presented by showing change in CTCAE severity grade from Baseline to worst grade post-Baseline. A shift table for hematology showing change in CTCAE severity grade from Baseline to worst Cycle 1 value will also be presented.

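### The SAP's by-visit laboratory window leaves the lipid table with a baseline row only and omits the combination-only C2D15 visit, and this narrowing of the protocol is not declared

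*SAP*

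**What the plan says.** Protocol 9.4.4.3 plans the by-visit laboratory tables without a visit limit: "Hematological and serum biochemistry and their changes from baseline will be summarized by dose level, by visit". SAP 6.6.4 adds coagulation but restricts the visits; the tables "will be summarized by dose level, by visit for visits from Baseline to C2D1 as well as EOT".

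SAP Table 4 puts lipids inside serum chemistry, whose list ends "glucose, sodium, potassium, chloride, calcium, magnesium, phosphate, full lipid panel". The note under that table gives the timing: "A full lipid panel, regardless of fasting status, will be performed on C1D1, C3D1" and C7D1, with none in the Monotherapy Phase 2. In the schedule (SAP 3.7), the row "Full Lipid Panel" is marked only at Cycle 1 Day 1 and at Day 1 of later cycles; its EOT cell is empty. The same schedule marks haematology and chemistry at a C2D15 visit that exists only for combination subjects.

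Other outputs have no C2D1 limit. SAP 6.6.4 plans shift tables "showing change in CTCAE severity grade from Baseline to worst grade post-Baseline", with a normal-range version for parameters that have no CTCAE scale. Treatment-emergent abnormalities are counted up to 30 days after the last dose. SAP 6.1 provides listings of case report form data.

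SAP section 8, which records departures from the protocol, does not mention the visit restriction.

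**The concern.** The SAP cuts the by-visit tables at a visit that precedes every post-baseline lipid draw. A programmer who follows 6.6.4 would produce a lipid table with a baseline row and nothing to compare it with. The SAP has change from baseline calculated for all post-baseline results, so these lipid changes would exist in the analysis data but be tabulated at no visit.

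Lipids have some scientific interest here. Protocol 2.2 reports lipid deposition in rat hepatocytes and attributes it most likely to the drug's anti-estrogenic action, on the ground that "estrogen plays an important role in lipid homeostasis within the liver". The C2D15 omission affects the one extra laboratory visit scheduled for combination subjects, and protocol 2.3.1 names low blood cell counts among the known effects of palbociclib.

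At stake is whether the report shows how large these changes were and when they occurred. The departure from protocol 9.4.4.3 is also undeclared.

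**Working it through.** The plan gives no figure to reproduce. The check sets scheduled draws against planned outputs.

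**Inputs.** Cycle length 28 days and visit schedule: SAP 3.7 (same as Protocol 1.3). By-visit window, lipid timing, shift and treatment-emergent rules: SAP 6.6.4. Lipid grades: SAP Appendix 11.4. By-visit tables use the nominal visit label (SAP 6.6.1), so visit-day tolerances do not move a draw into the window.

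**Nominal study day** = 28 × (cycle − 1) + day of cycle.

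- C2D1: 28 × 1 + 1 = 29 (last visit in the window before EOT)
- C2D15: 28 × 1 + 15 = 43
- C3D1: 28 × 2 + 1 = 57
- C7D1: 28 × 6 + 1 = 169

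| Scheduled draw | By-visit table | Worst-post-baseline shift table | Treatment-emergent summary | Listing |
|---|---|---|---|---|
| Lipids C1D1 (baseline) | Yes | As baseline | As baseline | Yes |
| Lipids C3D1 | No | Yes | Cholesterol and triglycerides | Yes |
| Lipids C7D1 | No | Yes | Cholesterol and triglycerides | Yes |
| Lipids at EOT | Not drawn | – | – | – |
| C2D15 haematology and chemistry (combination) | No | Yes | Where a grade exists | Yes |

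Post-baseline lipid draws in the by-visit window: 0 of 2.

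**Chemistry visits more generally**, for a monotherapy subject treated to C7D1 and leaving EOT aside: 3 in Cycle 1 (Days 1, 8, 15) + 6 (Day 1 of Cycles 2 to 7) = 9. In the window: 3 + 1 = 4. Outside: 9 − 4 = 5. C2D15 adds one more outside visit for combination subjects.

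**What the remaining summaries can show.** A treatment-emergent abnormality needs a worsening of at least one grade, or any grade if baseline is missing. Appendix 11.4 grades only high cholesterol and high triglycerides, so any other lipid component appears only as below, within or above range. For graded components the bands are wide. Triglyceride Grade 1 runs from above 1.71 to 3.42 mmol/L, and 3.42 / 1.71 = 2, so a value can almost double without a shift. Cholesterol Grade 2 spans 10.34 − 7.75 = 2.59 mmol/L. A worst-grade shift also merges C3D1 and C7D1, so timing is lost.

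The separate plasma cholesterol samples (C1D15 and Day 1 of Cycles 2 to 4, in Monotherapy Escalation and Expansion) do not clearly fill the gap, because SAP 6.6.4 has them listed only.

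**The case against.** The strongest reply is that the SAP already summarises these data in the form that matters. Treatment-emergent abnormalities are its stated focus, as in the protocol, and carry no C2D1 cut. The shift tables cover the whole post-baseline period, and the lipid grades are numeric bands, so they convey some magnitude. The same window is used for vital signs (SAP 6.6.5), which suggests a deliberate choice to keep tables short. SAP 6.1 allows summaries of change at each timepoint, and of best or worst change, as appropriate. Lipids are drawn regardless of fasting status, so mean triglyceride change would be noisy.

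Much of this stands, and it rules out several stronger readings. A reader might infer that lipid change is never summarised, or that C2D15 results are lost; the shift tables, abnormality summaries and listings show otherwise. A reader might also infer damage to the Monotherapy Expansion primary endpoint. That endpoint is the incidence of adverse events and laboratory abnormalities, which the by-visit tables do not supply. Nor do the documents say that the lipid draws were placed to show mean change by dose. They give timing only, and the rat finding is not linked to the panel.

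The reply does not justify a lipid by-visit table with no post-baseline row. The general permission in 6.1 is conditional, while 6.6.4 is specific and is what will be programmed. Use of the same window for vital signs does not explain its use for a panel whose post-baseline draws all lie outside it.

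**Conclusion.** The point holds as a minor gap in reporting. None of the 2 post-baseline lipid draws, and not the single C2D15 visit, reaches a by-visit table, so numeric changes there are not tabulated by visit. The cut is narrower than protocol 9.4.4.3 and undeclared in SAP section 8. The incidence-based safety results are largely unaffected; the absence of grades for other lipid components is a separate limit that the visit window does not cause.

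This rests on reading 6.6.4 literally, on lipids following the serum chemistry rules as Table 4 classifies them, and on the schedule as written, with no lipid draw at EOT. The lipid part does not apply to the Monotherapy Phase 2, where lipids are not collected, and the C2D15 part applies only to the combination parts.

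**What to change.** In SAP 6.6.4:

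1. Keep the Baseline-to-C2D1 and EOT rows for all dose levels.
2. Add lipid values and change from baseline at C3D1 and C7D1, by dose level, in the parts that collect lipids.
3. Add C2D15 haematology and chemistry for the combination parts.
4. Record any restriction that remains in section 8 as a change from protocol 9.4.4.3, with the reason.

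Do not attach a minimum of 5 subjects per dose level to the existing rows. Escalation cohorts can have 3 subjects (protocol 6.1.3 and 6.1.4), and such a rule would remove the by-visit Cycle 1 rows that they now receive, which cover the DLT period.

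The cost is SAP wording and a few more table rows, with no new data. The downside is small numbers at C7D1, so those rows should be read as descriptive only.

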6.6.5 Vital Signs

Vital signs include height (Baseline only), weight, temperature, pulse rate, respiration rate, systolic blood pressure and diastolic blood pressure, and oxygen saturation. Vital signs and their changes from Baseline will be summarized by visit for visits from Baseline to C2D1 as well as EOT.

6.6.6 Electrocardiogram (ECG)

The electrocardiogram assessment includes PR interval (msec), RR interval (msec), QRS interval (msec), QT interval (msec), QTcB interval (msec), and QTcF interval (msec). Change from Baseline will be calculated for all post-Baseline results. For ECG parameters measured in triplicates, the average of available measures will be computed for each timepoint.

If QTcB is missing and QT and either QTcB or RR is not missing, QTcB will be derived using one of the following formulas:

$$QTcB = QT / (QT / QTcF)^{3/2}$$

$$QTcB = QT / RR^{1/2}$$

The maximum post-Baseline QTcB value will be determined for each subject and categorized (≤ 450 , > 450 and ≤ 480 , > 480 and ≤ 500 , > 500).

The maximum increase from Baseline in QTcB value will be determined for each subject and categorized (≤ 30 , > 30 and ≤ 60 , > 60).

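### SAP 6.6.6: the rule for deriving a missing QTcB contradicts itself in its trigger and omits the conversion of RR from milliseconds to seconds

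*SAP*

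**What the plan says.** SAP 6.6.6 lists the ECG intervals with their units, among them "RR interval (msec), QRS interval (msec), QT interval (msec), QTcB interval (msec), and QTcF interval (msec"), so RR and QT are both in milliseconds. A missing QTcB is to be filled in on this condition: "If QTcB is missing and QT and either QTcB or RR is not missing". When it is met, "QTcB will be derived using one of the following formulas". The first formula is QT/(QT/QTcF)^(3/2) and the second is QT/RR^(1/2). No order of preference is given and no conversion of RR is stated.

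Two summaries then use QTcB. "The maximum post-Baseline QTcB value will be determined for each subject and categorized" into ≤450, >450 to 480, >480 to 500 and >500. "The maximum increase from Baseline in QTcB value will be determined for each subject and categorized" into ≤30, >30 to 60 and >60. The section gives no lower plausibility limit for a derived value and sets no categories for QTcF. On replicates it says: "For ECG parameters measured in triplicates, the average of available measures will be computed for each timepoint".

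**The concern.** The trigger names QTcB twice, once as missing and once as possibly present. The first formula needs QTcF, which the trigger does not mention, so QTcF was evidently meant in the second place.

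The RR formula is Bazett's, which takes RR in seconds. With RR in milliseconds it returns a number that cannot be a QTc interval, yet the lowest bands have no floor and will accept it.

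What is at stake is the categorical QT safety table. QTcB is the only correction that is categorised, so a wrong derived value can change a subject's band for the maximum or for the increase from baseline.

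**Working it through.** **Inputs.** The trigger, both formulas, the units, the bands and the triplicate rule come from SAP 6.6.6. The section states no numerical result to reproduce. The documents give no ECG data, so the QT and RR values below are assumed for illustration.

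**1. The trigger.** With QTcB missing and QT present:

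| QTcF present | RR present | Derived as written | Derived with QTcF in the trigger |
|---|---|---|---|
| no | no | no | no |
| no | yes | yes | yes |
| yes | no | **no** | **yes** |
| yes | yes | yes | yes |

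The two versions differ only for a record with QTcF but no RR. The protocol's ECG section (8.2.1.3) names ventricular rate, PR, QRS, QT and QTc but not RR, so such records are possible.

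**2. The unit.** Bazett: QTcB = QT/√(RR in seconds). Since RR in ms = 1000 × RR in seconds, QT/√(RR in ms) = QTcB/√1000 = QTcB/31.62, whatever the values of QT and RR.

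| QT (ms) | RR (ms) | QT/√(RR/1000) | QT/√RR as printed |
|---|---|---|---|
| 400 | 800 | 447.2 | 14.1 |
| 440 | 800 | 491.9 | 15.6 |
| 440 | 700 | 525.9 | 16.6 |
| 520 | 1000 | 520.0 | 16.4 |

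**3. The two formulas against each other.** Fridericia: QTcF = QT/(RR in seconds)^(1/3). Hence (QT/QTcF)^(3/2) = (RR in seconds)^(1/2), and the QTcF-based formula equals Bazett exactly. For QT 400 and RR 800, QTcF = 430.9 and 400/(400/430.9)^(3/2) = 447.2. The printed RR formula gives 14.1 on the same record.

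**4. Which band.** Over an assumed wide range (QT 300 to 700 ms, RR 300 to 2000 ms) the printed RR formula runs from 300/√2000 = 6.7 to 700/√300 = 40.4. All of these fall in ≤450. At RR 1000, passing 450 would need a QT of 450 × √1000 = about 14,230 ms.

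**5. Effect on the tables.**

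- *Affected post-baseline value.* Take a recorded baseline of 420 and a post-baseline record with QT 440 and RR 700. Correct: 525.9 (>500) and a change of +105.9 (>60). As printed: 16.6 (≤450) and 16.6 − 420 = −403.4 (≤30).
- *Affected baseline.* Take a baseline with QT 400 and RR 900, and a recorded post-baseline value of 430. Correct: 430 − 400/√0.9 = +8.4 (≤30). As printed: 430 − 400/√900 = +416.7 (>60).
- *One affected replicate of three.* The SAP does not say whether derivation comes before averaging. If it does, and the other two replicates are 525.9, the mean is (2 × 525.9 + 16.6)/3 = 356.1, which is in ≤450.

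**The case against.** The intended meaning can be recovered. The SAP glossary defines QTcB as the Bazett adjustment, for which seconds are the usual unit, and the companion formula agrees only on that reading. A competent programmer may well convert RR without being told. QTcB is itself a listed ECG item, so this is a fallback that may be used rarely or never. SAP section 4 refers to data validation specifications and a programming quality-control plan, and a QTcB of 14 ms is easy to spot in a listing. ECG results are descriptive, changes from baseline also cover QT and QTcF, and under the protocol the investigator or a qualified designee reviews every ECG. On-study review therefore does not depend on this derivation.

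All of this stands as a limit on the likely harm. It does not remove the printed unit, the 31.6-fold conflict between two formulas offered as interchangeable, or the contradiction in the trigger. The contents of the validation and quality-control plans are not in the documents.

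Stronger readings are tempting, and the text does not support them:

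- A reader might infer that the QTcF formula can never be used. It is blocked only when RR is missing. With both present, the wording allows either formula.
- A reader might infer that every record with QTcB missing is wrong. The unit error needs RR present, the RR formula chosen, and RR left in milliseconds.
- A reader might infer that the error always hides prolongation. An affected baseline does the opposite and produces a conspicuous false increase. Because the tables use the maximum, a correctly recorded high value elsewhere for that subject still counts.
- A reader might take ≤450 as labelled normal. The SAP gives it only as the lowest band.

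**Conclusion.** The rule is wrong as written in two places. Read literally, the trigger leaves QTcB missing on records that have QT and QTcF but no RR. Applied literally, the RR formula gives values too small by exactly √1000 = 31.6, and so disagrees with the QTcF formula on the same record.

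An affected post-baseline value lands in the lowest bands, and changes the subject's category for the maximum only if that record would have set it. An affected baseline produces a false increase above 60.

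The factor and the contradiction follow from the SAP's text and the standard Bazett and Fridericia definitions. The band examples rest on assumed QT and RR values. The number of affected records is not given and could be zero, so the documents do not show that any reported table is wrong. This should be corrected because the rule itself gives a wrong result and the repair is very small.

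**What to change.** Replace the rule in SAP 6.6.6 with: *If QTcB is missing and QT and either QTcF or RR is not missing, QTcB = QT/(RR/1000)^(1/2) with RR in msec if RR is available; otherwise QTcB = QT/(QT/QTcF)^(3/2).*

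The two corrected formulas agree up to rounding, so the order of preference is there only for reproducibility.

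Then check the analysis program against this text. If it used RR in milliseconds, or skipped records with QTcF but no RR, re-derive those values and rerun the two QTcB tables. The cost is a few words in one section and a short program check. No new data are needed.

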AUC _{last}	Area under the plasma concentration-time curve from zero to the time of last quantifiable plasma concentration
AUC _{tau}	Area under the concentration-time curve from the time of dosing to the end of the dosing interval ($\tau = 12$ or 24 hours)
β -hCG	Beta-human chorionic gonadotropin
BID	Twice daily
BUN	Blood urea nitrogen
CBR	Clinical benefit rate
CI	Confidence interval
C ₀₋₁₂	Concentration at the end of the dosing interval (BID dosing; ZN-c5 only)
C ₀₋₂₄	Concentration at the end of the dosing interval QD dosing only
C _{ave}	Average steady-state plasma concentration
CL/F	Apparent total plasma clearance after a single dose oral administration
CL _{ss} /F	Apparent total plasma clearance after multiple dose oral administration
C _{max}	Maximum observed plasma concentration after a single dose administration
C _{max,ss}	Maximum observed plasma concentration after multiple dose administration
CPK	Creatine phosphokinase
CR	Complete response

Statistical Analysis Plan

Protocol No. ZN-c5-001

Revision 00: 17Feb2023

(Page 7 of 47)

GLOSSARY OF ABBREVIATIONS

Abbreviation	Term
CrCl	Creatinine clearance
C_{trough}	Concentration at the end of the dosing interval (tau = 12 or 24 hours)
CV%	Coefficient of variation
DLT	Dose-limiting toxicity
DOOR	Duration of response
ECG	Electrocardiogram
ECOG	Eastern Cooperative Oncology Group
eCRF	Electronic case report form
ER	Estrogen Receptor
FAS	Full analysis set
FES	^{18}F -fluoroestradiol
GGT	Gamma-glutamyl-transferase
HER2	Human Epidermal Growth Factor Receptor-2
ICH	International Council for Harmonisation
INR	International normalized ratio
λ_z (Lambda z)	Terminal elimination phase rate constant
LLN	Lower limit of normal
MedDRA	Medical Dictionary for Regulatory Activities
MTD	Maximum tolerated dose
NA	Not applicable
NCI CTCAE	National Cancer Institute Common Terminology Criteria for Adverse Events
ORR	Objective response rate
OS	Overall Survival
PD	Disease progression
PET	Positron emission tomography

Statistical Analysis Plan

Protocol No. ZN-c5-001

Revision 00: 17Feb2023

(Page 8 of 47)

GLOSSARY OF ABBREVIATIONS

Abbreviation	Term
PFS	Progression-free survival
PK	Pharmacokinetic(s)
PR	Partial response
PS	Performance Status
PT	Prothrombin time
QD	Once daily
QTcB	QT interval adjusted using Bazett's formula
QTcF	QT interval adjusted using Fridericia's formula
RAUC	AUC accumulation ratio
RECIST	Response Evaluation Criteria in Solid Tumors
RP2D	Recommended Phase 2 dose
SAE	Serious Adverse Event

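### QT outlier categories are planned for Bazett only, although Fridericia is also in the ECG assessment, so a subject's category depends on heart rate

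*SAP*

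**What the plan says.** SAP section 6.6.6 names PR, RR, QRS, QT, QTcB and QTcF as the ECG parameters. The glossary defines QTcF as the "QT interval adjusted using Fridericia's formula". For every parameter, "Change from Baseline will be calculated for all post-Baseline results".

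Both outlier analyses use QTcB only:

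- On the absolute scale, the plan states: "The maximum post-Baseline QTcB value will be determined for each subject and categorized". Its cuts are 450, 480 and 500 ms.
- On the change scale, the plan states: "The maximum increase from Baseline in QTcB value will be determined for each subject and categorized". Its cuts are 30 and 60 ms.

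No other section plans categories for QTcF. No reason is given for using Bazett alone, and SAP section 8 (changes from the protocol) does not mention the choice. The protocol does not settle it either. Exclusion criterion 14 (section 5.2) and the ECG section (8.2.1.3) refer to QTc without naming a correction.

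Section 6.6.6 also gives two formulas for filling in a missing QTcB, one from QT and QTcF and one from QT and RR. It gives no rule for a missing QTcF.

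**The concern.** Two corrections are available and only one is categorised. By the SAP's own formulas the two agree only at 60 bpm, so a count of subjects above 450, 480 or 500 ms partly reflects the heart rate at which the ECGs were taken. The same applies to the count with an increase above 30 ms if heart rate differs between baseline and follow-up.

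Two design features make this harder to see in the output. First, the analysis takes each subject's maximum, and SAP section 6.6.1 makes unscheduled assessments eligible for worst-case analyses. With QTcF flat, the largest QTcB is the one recorded at the fastest rate, so the effect does not average out within a subject. Second, every cohort receives ZN-c5, so no untreated group is available against which a heart-rate effect could be judged.

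What is at stake is the reading of one safety table for a drug that the protocol (section 2.3.3) describes as first-in-human.

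**Working it through.** There is no stated figure to reproduce. The check uses the formulas in SAP section 6.6.6.

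**Formulas.** With RR = 60/HR in seconds, the SAP gives QTcB = QT / RR^(1/2) and QTcB = QT / (QT/QTcF)^(3/2). Setting them equal gives QT/QTcF = RR^(1/3), so QTcF = QT / RR^(1/3). Then

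QTcB / QTcF = RR^(1/3 − 1/2) = RR^(−1/6) = (HR/60)^(1/6).

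Numerical check at QT 360, 75 bpm (RR 0.8 s): QTcF = 387.8. The first route gives 360/0.8^(1/2) = 402.5, and the second gives 360/(360/387.8)^(3/2) = 402.5.

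**Assumed inputs.** Heart rate 50 to 120 bpm and QTcF 420 to 460 ms. Neither range comes from the documents.

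| HR (bpm) | Factor | QTcB if QTcF 420 | QTcB if QTcF 440 | QTcB if QTcF 460 | QTcF at which QTcB = 450 / 480 / 500 |
|---|---|---|---|---|---|
| 50 | 0.970 | 407.4 | 426.8 | 446.2 | 463.9 / 494.8 / 515.4 |
| 60 | 1.000 | 420.0 | 440.0 | 460.0 | 450.0 / 480.0 / 500.0 |
| 70 | 1.026 | 430.9 | 451.5 | 472.0 | 438.6 / 467.8 / 487.3 |
| 80 | 1.049 | 440.6 | 461.6 | 482.6 | 428.9 / 457.5 / 476.6 |
| 90 | 1.070 | 449.4 | 470.8 | 492.2 | 420.6 / 448.6 / 467.3 |
| 100 | 1.089 | 457.3 | 479.1 | 500.9 | 413.3 / 440.8 / 459.2 |
| 110 | 1.106 | 464.6 | 486.8 | 508.9 | 406.8 / 433.9 / 452.0 |
| 120 | 1.122 | 471.4 | 493.9 | 516.3 | 400.9 / 427.6 / 445.4 |

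**Maximum-value bins.** The rate at which a constant QTcF crosses a cut T is HR = 60 × (T/QTcF)^6. For QTcF 440:

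- 450 is crossed at 60 × (450/440)^6 = 68.7 bpm.
- 480 is crossed at 60 × (480/440)^6 = 101.1 bpm.

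In the other direction, QTcF 460 at 50 bpm gives 460 × 0.9701 = 446.2, which falls in the lowest bin although QTcF is above 450.

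**Maximum-increase bins.** With QTcF constant, the apparent increase is QTcF × [(HR1/60)^(1/6) − (HR0/60)^(1/6)]. For QTcF 420:

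- From 60 to 100 bpm: 420 × (1.0889 − 1) = 37.3 ms, which is in the middle bin.
- From 70 to 100 bpm: 26.4 ms, which is in the lowest bin.
- The 30 ms cut is reached at 90.8 bpm from a baseline of 60, or 104.8 bpm from a baseline of 70.
- The 60 ms cut is reached at 133.7 bpm from a baseline of 60, or 153.0 bpm from a baseline of 70.

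**Stable heart rate.** If the rate is 90 bpm at both times, the QTcB change is 1.0699 times the QTcF change. The 30 ms cut on QTcB then corresponds to 30/1.0699 = 28.0 ms on QTcF, and the 60 ms cut to 60/1.0699 = 56.1 ms. That is a small shift.

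**Units.** RR is listed in msec, but the formula needs seconds. QT 360 with RR entered as 800 gives 360/800^(1/2) = 12.7, against 402.5 with RR 0.8.

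**The case against.** The strongest reply is that the algebra shows only that the two corrections differ away from 60 bpm. It does not show which is right. A reader might infer that QTcB outliers at fast rates are false signals and that slow-rate ones are missed. The documents do not support that, because no section treats QTcF as the reference. The SAP's reference list includes a QT guideline, but its content is not in the documents. What stands is narrower: the result depends on the correction, and only one is categorised.

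A reader might also set the gap between formulas at one time point (457.3 − 420 = 37.3 ms at 100 bpm) against the 30 ms change bin. That comparison fails, because the change bin is within subject. The two figures coincide above only because the baseline was put at 60 bpm, where the formulas agree. With a stable rate the gap largely cancels.

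A third tempting reading is that these cuts are safety thresholds with consequences. They are display bins. SAP section 6.6 presents safety data descriptively, and no dose-limiting toxicity criterion, discontinuation rule or endpoint refers to them. The protocol's 480 ms limit is an entry criterion and is unaffected.

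The plan also has partial cover. QTcF change from baseline is calculated, SAP section 6.1 allows summaries of worst change as appropriate, pulse rate is summarised (6.6.5), and the investigator or a designee reviews all ECGs (protocol 8.2.1.3). Protocol section 2.2 reports no cardiovascular effects in dogs, and no section says that either drug changes heart rate. All this stands, and it limits the weight of the point. It does not supply QTcF outlier categories.

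**Conclusion.** The point holds as a minor improvement to a descriptive safety display. The SAP applies its maximum-value and maximum-increase categories to QTcB only, and by its own formulas the resulting category depends on heart rate when QTcF is constant.

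At the assumed values, heart rate alone can move a subject across the 450, 480, 500 and 30 ms cuts. It is unlikely to do so for the 60 ms cut. The change bins are affected materially only if heart rate shifts from baseline.

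How many subjects this would touch cannot be estimated, because the documents contain no heart-rate data. No primary endpoint, sample size or decision rule is affected.

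**What to change.** In SAP section 6.6.6:

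1. Apply the same maximum-value (450/480/500 ms) and maximum-increase (30/60 ms) categories to QTcF, and report them beside those for QTcB.
2. Add a rule for missing QTcF: QTcF = QT / RR^(1/3) with RR in seconds or, where RR is missing, QTcF = QT / (QT/QTcB)^(2/3). Without it the new table may have avoidable gaps.
3. Correct the condition for deriving a missing QTcB. It currently names QTcB itself as one of the alternative inputs, which is circular. The first formula shows that QTcF is meant, so it should require QT and either QTcF or RR.
4. State that RR, listed in msec, is converted to seconds before either formula is used.

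The cost is one extra table and one derivation line, plus two wording corrections. No new data are needed, because QTcF, QT and RR are already in the ECG assessment.
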